6.7.4 Minimal Residual Disease Analysis

Cryopreserved mononuclear cells from bone marrow aspirate and/or peripheral blood will be analyzed for minimal residual disease assays via flow cytometry, DNA or RNA PCR.

6.8 Assessment of Safety

Any patient who receives pembrolizumab treatment on this protocol will be evaluable for toxicity. Each patient will be assessed periodically for the development of any toxicity according to the Time and Events table (6.0). Toxicity will be assessed according to NCI CTCAE v4. Toxicities will be characterized in terms of seriousness, causality, toxicity grading, and action taken with regard to trial treatment.

For subjects receiving treatment with pembrolizumab, all AEs of unknown etiology associated with pembrolizumab exposure should be evaluated to determine if it is possibly an event of clinical interest (ECI) of a potentially immunologic etiology (termed immune-related adverse events, or irAEs); see the separate ECI guidance document (provided as a document separate from this protocol) regarding the identification, evaluation and management of potential irAEs.

Please refer to section 7.0 for detailed information regarding the assessment and recording of AEs.

6.9 Assessment of Efficacy

Patients who have received pembrolizumab within the induction phase (cycle) will be evaluable for assessment of response and progression. Efficacy of treatment will be assessed by a bone marrow biopsy at the time of hematologic recovery (i.e., absolute neutrophil count $\geq 1,000/\text{mcL}$ and platelet count

$\geq 100,000/\text{mcL}$), or by day 45 +/- 2 days of induction treatment, whichever occurs first. Response will be assessed by standard international criteria proposed by the European LeukemiaNet Guidelines in AML.²¹

Complete remission (CR): Bone marrow blasts $< 5\%$; absence of Auer rods; absence of extramedullary disease; absolute neutrophil count $\geq 1,000/\text{mcL}$; platelet count $\geq 100,000/\text{mcL}$; independence of red cell transfusions

Complete remission with incomplete recovery (CRi): All CR criteria except for residual neutropenia ($\leq 1,000/\text{mcL}$) or thrombocytopenia ($\leq 100,000/\text{mcL}$) plus independent of platelet transfusions.

Partial response (PR): bone marrow blasts 5-25% and decrease of pretreatment bone marrow blast % by $\geq 50\%$; all hematologic criteria of CR.

Patients who achieve a PR to induction phase and then achieve CR after maintenance pembrolizumab will be assessed as an overall CR to study treatment.

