1.0 BACKGROUND AND RATIONALE

1.1 Study Synopsis

This is an open-label, single arm, multicenter phase 2 study of standard salvage high dose cytarabine (HiDAC) on days 1 through 5 followed by a single dose of the humanized monoclonal antibody targeted against cell surface receptor programmed cell death-1 (PD-1), pembrolizumab, on day 14 as induction therapy in patients with relapsed and refractory acute myeloid leukemia (AML). Patients who achieve at least a partial response (PR) post-induction will continue on pembrolizumab every 3 weeks for up to 1 year of maintenance therapy. We plan to enroll 37 patients in a Simon's two-stage design.

The hypothesis of this study is that HiDAC followed by pembrolizumab will be effective in relapsed and refractory AML with a combined complete remission (CR)/CR with incomplete recovery (CRi) rate of $\geq 40\%$, superior to a historical control of 20%. We also hypothesize that the rate of unacceptable toxicity associated with HiDAC followed by pembrolizumab will not significantly exceed 20% (see section 2.4.2). Secondary endpoints include toxicity of this combination when used as induction, overall objective response rate (CR+CRi +PR) post-induction, toxicity of pembrolizumab maintenance in those patients with a response after induction, and progression-free survival (PFS), relapse-free survival (RFS) and overall survival (OS) in patients who receive maintenance pembrolizumab. We will also explore for an association between potential immune biomarkers and clinical outcomes with pembrolizumab. The overarching goals of these correlative studies are: 1) to identify and characterize mechanisms involved in T cell dysfunction in AML, 2) to identify potential predictive biomarker candidates to allow better selection of AML patients who may benefit from pembrolizumab, and 3) to identify new pathways that could be targeted to enhance the efficacy of pembrolizumab in AML.

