8.0 STATISTICAL CONSIDERATIONS

8.1 Study Design and Sample Size

This is a multi-center prospective open-label single arm phase 2 study assessing the activity of age-adjusted HiDAC (<60 years: 2 gm/m² IV Q12hours days 1-5; ≥60 years: 1.5 gm/m² IV Q12hours days 1-5) salvage induction treatment followed by pembrolizumab 200 mg IV on day 14 for relapsed or refractory AML patients.

The subjects who achieve a response (CR, CRi, or PR) to induction phase HiDAC followed by pembrolizumab 200 mg IV on day 14, as assessed by standard international European LeukemiaNet Guidelines in AML,²¹ will receive pembrolizumab 200 mg IV Q3weeks of maintenance therapy beginning 10-30 days following full hematologic recovery from induction phase. Maintenance treatment will continue until disease progression, toxicity, physician and/or patient discretion, or up to 1 year of treatment.

Simon's like two-stage design with relaxed stopping for futility will be used.⁵³ The null hypothesis that the true CR rate (CR/CRi) for HiDAC followed by pembrolizumab is 20% will be tested against a one-sided alternative hypothesis. In this study, "relaxed stopping" refers to inclusion of PR in the first stage as some of these PRs may convert to a CR during maintenance. In the first stage, 19 patients will be enrolled. If the number of patients who achieve a CR/CRi plus the number of patients with PR is equal to 4 or fewer in these 19 patients, the study will be stopped. Otherwise, 18 additional patients will be enrolled for a total of 37 patients. The null hypothesis will be rejected if 12 or more CR/CRi's are observed in 37 patients.. Assuming that the PR rate has a uniform distribution, Uniform (0, 0.05), under H₀, this design yields a type 1 error rate of at most 5% and power of at least 84% when the true CR rate for HiDAC followed by pembrolizumab is 0.4.

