8.3 Data Analysis Plans

The primary endpoint of this study is the overall CR rate (CR+CRi) after HiDAC salvage followed by pembrolizumab on day 14. Responses will be assessed by standard international European LeukemiaNet Guidelines.²¹

Secondary endpoints include the following:

- Rates of unacceptable toxicity defined as any drug-related grade 3 non-hematologic toxicity (exceptions: fever, rash, infection, infusion reactions, nausea, fatigue and anorexia) lasting for >7days despite supportive care, or any drug-related grade ≥ 4 non-hematologic toxicity (excluding infection)
- Clinician assessed toxicity of HiDAC followed by pembrolizumab will be classified and graded according to NCI CTCAE, version 4.0.
- Objective overall response rates will be defined as PR+CR+CRi as determined by international European LeukemiaNet Guidelines in AML.²¹
- Clinician assessed toxicity of pembrolizumab maintenance will be classified and graded according to NCI CTCAE, version 4.0
- RFS will be defined as time from day 1 of CR/CRi to relapse or death from any cause.
- PFS will be defined as time from day 1 of response (i.e., PR/CR/CRi) to progression or death from any cause.
- OS will be defined as time from day 1 of treatment until date of last known follow up or death of any cause.

Survival distributions will be summarized using the method of Kaplan and Meier. We will report median time where possible. All demographic and analytic data will be summarized by descriptive statistics. Categorical data will be summarized using frequency tables while summary statistics such as means, medians, standard deviation, range, etc., will be provided for continuous data. 95% confidence intervals will be reported as well.

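### The primary CR/CRi count may include PR-to-CR conversions on maintenance, while the 20% benchmark appears to be induction-only; the plan should fix one count, one cut-off and a matching null.

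*Combined protocol and SAP*

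**What the plan says.** Section 8.3 states: "The primary endpoint of this study is the overall CR rate (CR+CRi) after HiDAC salvage followed by pembrolizumab on day 14". Section 2.1 words the primary objective in the same way, around HiDAC and the day-14 dose. Section 2.4.1 gives the endpoint as the CR+CRi rate and names no time point.

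Section 6.9 places the efficacy marrow at hematologic recovery or day 45 ± 2, whichever is first. It then adds: "Patients who achieve a PR to induction phase and then achieve CR after maintenance pembrolizumab will be assessed as an overall CR to study treatment". No time limit is attached.

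Section 8.1 sets the test: "The null hypothesis that the true CR rate (CR/CRi) for HiDAC followed by pembrolizumab is 20% will be tested against a one-sided alternative hypothesis". On stage 1 it says "In the first stage, 19 patients will be enrolled"; if the sum of CR/CRi and PR "is equal to 4 or fewer in these 19 patients, the study will be stopped". Otherwise 18 more patients enter, and the null is rejected at 12 or more CR/CRi among 37. PR enters the stage-1 count because some PRs may become CRs on maintenance. With the PR rate uniform on 0 to 0.05 under the null, "this design yields a type 1 error rate of at most 5% and power of at least 84" percent "when the true CR rate for HiDAC followed by pembrolizumab is 0.4". No conversion rate is given.

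Section 1.1 presents the target as "superior to a historical control of 20" percent. The supporting data in section 1.3 are response rates of 15–20% for cytarabine alone and about 20% CR for physician's choice. No maintenance treatment is described for those arms. Maintenance lasts up to 1 year in section 8.1 and up to 2 years (34 cycles) in section 4.3.

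**The concern.** A single-arm test against a fixed rate is interpretable only if the observed count and the benchmark measure the same thing. Sections 2.1 and 8.3 read as a post-induction rate. Section 6.9, together with the reason section 8.1 gives for relaxed stopping, reads as a best response that includes later conversion. The benchmark seems to come from reinduction chemotherapy.

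Two things are at stake. If conversions are added to a benchmark that does not contain them, the trial can succeed more often than 5% of the time when induction is no better than history. And because neither the count nor its closing date is fixed, the choice could be made after the data are seen. With a threshold of 12, one or two late conversions could decide the result.

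**Working it through.** **Inputs.** From section 8.1: stage 1 n = 19, continue if CR/CRi + PR ≥ 5; stage 2 n = 18; reject if CR/CRi ≥ 12 of 37; null 0.20; alternative 0.40; PR rate q ~ Uniform(0, 0.05). The share c of PRs that convert is not in the documents and is varied from 0 to 1.

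**Formula.** Let p be the true induction CR/CRi rate, so the counted rate is f = p + cq. In stage 1, X is the number of counted CRs (including PRs that later convert) and Y the number of PRs that do not convert. Conversion does not change the futility count, which is X + Y. Then

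P(success) = Σ over x + y ≥ 5 of [19! / (x! y! (19−x−y)!)] · f^x · (q(1−c))^y · (1−p−q)^(19−x−y) · P(Bin(18, f) ≥ 12−x).

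**Step 1: the plan's own figures (c = 0).**
- At p = 0.20: 4.71% (q = 0), 4.85% (q = 0.025), 4.96% (q = 0.05); average 4.85%.
- At p = 0.40: 84.1% (q = 0) to 85.8% (q = 0.05); average 85.1%.

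Both stated bounds reproduce. There is little slack: with q = 0, the error reaches 5% at a counted rate of 20.2%.

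**Step 2: conversions inside the 20%.** Set p = 0.20 − cq, so that f = 0.20. For q = 0.025 or 0.05 and c = 0.5 or 1, the rejection probability is 4.7% to 4.9%. The stated 5% holds.

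**Step 3: conversions on top of a 20% induction rate (p = 0.20).**

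| Share converting | Averaged over q | q = 0.025 | q = 0.05 |
|---|---|---|---|
| 0 | 4.85% | 4.9% | 5.0% |
| 25% | 5.9% | 5.9% | 7.3% |
| 50% | 7.2% | 7.1% | 10.2% |
| 100% | 10.4% | 9.9% | 17.9% |

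**Step 4: how many PRs this involves.** Expected PRs in 37 patients: 37 × 0.025 = 0.93 at the mean PR rate, and 37 × 0.05 = 1.85 at the top of the range.

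**Step 5: power if only post-induction CR/CRi is tested.** If 2.5 of the 40 points were to come from conversions (p = 0.375, q = 0.025, c = 0), power is 77.0%. If 5 points were (p = 0.35, q = 0.05), it is 67.4%.

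**The case against.** The strongest reply is that section 8.1 places the null on the CR/CRi rate of the regimen. If the endpoint includes conversions, so does the 20%, and step 2 confirms the stated error. The rates above 5% in step 3 arise at counted rates above 20%, outside the null as written. This stands. A reader might infer that the type I error in section 8.1 is wrong; the documents do not support that. What the reply does not settle is interpretation: if the 20% includes conversions, it no longer matches the data cited for it, and rejection would not by itself show superiority to the historical control named in section 1.1.

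Second, counting conversions is deliberate. The stage-1 rationale makes most sense if they also count at the end, so sections 6.9 and 8.1 agree with each other. The tension is with sections 2.1 and 8.3, and even 8.3 speaks of an overall CR rate. This also stands, and it is why dropping conversions is not the only acceptable repair.

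Third, the excess may be small or absent. Few PRs are expected, and not every PR patient will qualify for maintenance under section 4.3. The true induction rate may also be below 20%: at 17.5%, averaged over the PR range, P(success) is 1.9%, 3.2% and 5.1% for 0, 50% and 100% conversion. Some of the cited rates are CR without CRi, though, which limits that comparison. If pembrolizumab itself produces the conversions, counting them may be detecting activity. All this bears on size, not on whether the count should be fixed in advance.

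Finally, one might infer that the primary result never closes. Maintenance is capped, so it does close; but no date is set, and the cap differs between sections.

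**Conclusion.** The point holds as a mismatch between endpoint and benchmark, not as an arithmetic error. The 5% and 84% in section 8.1 are right when null and test use one count. If the 20% is induction-only and conversions are added, the average chance of success is 5.9% to 10.4% for conversion shares of 25% to 100%, and 17.9% at the extreme.

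This rests on three assumptions: a true induction rate of exactly 20%; the plan's own PR range; and a conversion share that the documents do not give, with zero conversion returning 4.85%. That the 20% is induction-only is inferred from the cited chemotherapy arms; the documents do not say so. The change is worth making because it is cheap and prevents a choice of count after the data are known.

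**What to change.** Reconcile sections 2.1, 6.9, 8.1 and 8.3 so that one count enters the 12-of-37 rule. Two routes are defensible.

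**(a) Post-induction count.** Test CR/CRi at recovery or day 45, with the 30-day count-recovery window already in section 4.2, and report PR-to-CR conversions as a secondary result. The null then matches the cited data and the 5% bound holds. The cost is power: about 77% if 2.5 points of the 40% were to come from conversions, about 67% if 5 points were. PR can stay in the stage-1 count, but its rationale must be reworded, since conversions would no longer count at the end.

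**(b) Count including conversions.** Keep section 6.9 and set a fixed assessment cut-off. State that the 20% null refers to this count, or give the error rate against an induction-only 20%. Report the post-induction CR/CRi rate with its confidence interval alongside. The cost is wording, plus waiting for the cut-off before the primary result is final.

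Under either route, reconcile the maintenance duration between sections 8.1 and 4.3; under (b) it also bounds the conversion window.

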6.9.1 Progression-Free Survival and Relapse

Progression-free survival (PFS) will be defined as time from response (i.e., PR/CR/CRi) until disease progression or death. In patients who achieve a PR after Induction Phase, progression will be defined as $> 50\%$ increase in bone marrow blast % over baseline from beginning Maintenance Phase with a minimum 15% point increase in blasts, loss of PR (i.e., $> 25\%$ bone marrow blasts), leukemia-related complications such as transfusion dependence, presence of extramedullary disease (including symptomatic CNS disease), or circulating blasts. This is consistent with European LeukemiaNet Guidelines 2017.² Progression will be defined as relapse (i.e., $\geq 5\%$ bone marrow blasts) in patients who initially achieved a CR or CRi with induction phase. Patients who undergo an allogeneic stem cell transplant will be censored for PFS.

6.9.2 Relapse-Free Survival

Relapse-free survival (RFS) will be defined as time from CR or CRi until relapse or death. Relapse will be defined as bone marrow blasts $\geq 5\%$ in a patient who initially achieved a CR or CRi after induction phase. Patients who undergo an allogeneic stem cell transplant will be censored for RFS.

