3.2 Exclusion Criteria

Patients meeting any of the following exclusion criteria will not be able to participate in this study:

3.2.1 Is currently participating in or has participated in a study of an investigational agent or using an investigational device within 4 weeks of the first dose of treatment.

3.2.2 Has a diagnosis of immunodeficiency or is receiving systemic steroid therapy or any other form of immunosuppressive therapy within 7 days prior to the first dose

of HiDAC treatment. **NOTE:** use of steroid eye drops starting at the time of HiDAC administration is allowed.

[figure not shown]
- 3.2.3** Has a known history of active TB (Bacillus Tuberculosis)
- 3.2.4** Hypersensitivity to pembrolizumab or any of its excipients
- 3.2.5** Has had a prior monoclonal antibody within 4 weeks prior to study Day 1 or who has not recovered (i.e., \leq Grade 1 or at baseline) from adverse events due to agents administered more than 4 weeks earlier.
- 3.2.6** Has had prior chemotherapy, targeted small molecule therapy, or radiation therapy within 2 weeks prior to study Day 1 or who has not recovered (i.e., \leq Grade 1 or at baseline) from adverse events due to a previously administered agent.
- Note: Subjects with \leq Grade 2 neuropathy are an exception to this criterion and may qualify for the study.
 - Note: If subject received major surgery, they must have recovered adequately from the toxicity and/or complications from the intervention prior to starting therapy.
- 3.2.7** Has a known additional malignancy that is progressing or requires active treatment. Exceptions include basal cell carcinoma of the skin, squamous cell carcinoma of the skin that has undergone potentially curative therapy, or in situ cervical cancer that has undergone potentially curative therapy.
- 3.2.8** Has known active central nervous system (CNS) leukemia; subjects with previously treated CNS disease may participate provided they are stable (without evidence of active disease by imaging for at least 4 weeks prior to the first dose of treatment, and any neurologic symptoms have returned to baseline), have no evidence of new or enlarging brain metastases, and are not using steroids for at least 7 days prior to D1 of treatment.

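### After CR/CRi, an extramedullary relapse with marrow blasts below 5% is not an RFS or PFS event, and the event rule for PR-to-CR converters is unclear

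*Combined protocol and SAP*

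**What the plan says.** **Response (6.9).** CR requires "absence of extramedullary disease" alongside the marrow and blood-count criteria. CRi is CR apart from the counts, so the extramedullary criterion applies to it too. A patient in PR after induction who reaches CR on maintenance "will be assessed as an overall CR to study treatment".

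**Progression after PR (6.9.1).** Besides the marrow rules, the events are "leukemia-related complications such as transfusion dependence" and "presence of extramedullary disease (including symptomatic CNS disease), or circulating blasts".

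**Progression or relapse after CR/CRi.** For PFS, 6.9.1 uses marrow blasts of 5% or more "in patients who initially achieved a CR or CRi with induction phase". For RFS, 6.9.2 says "Relapse will be defined as bone marrow blasts" of 5% or more "in a patient who initially achieved a CR or CRi after induction phase". Death is an event for both endpoints, and allogeneic transplant censors both.

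**Endpoint sections.** 2.4.2 and 8.3 start RFS at CR/CRi without tying it to induction, and neither defines relapse. Objective 2.2.5 limits RFS and PFS to patients on maintenance.

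**CNS disease and follow-up.** Under 3.2.8, "subjects with previously treated CNS disease may participate provided they are stable". Section 4.5.2 permits intrathecal chemotherapy for CNS disease on maintenance while a clinical response continues. Section 4.7 follows patients for progression as well as survival in the later years. Section 6.6 and footnote 5 of the Time and Events table restrict the later visits to subsequent treatments, related SAEs and survival status.

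**The concern.** The definition of relapse should mirror the definition of remission. Here a patient can stop meeting the CR criteria, because leukemia has appeared outside the marrow, without having an event in either endpoint that measures loss of response. The same finding in a PR patient is progression. The event is then recorded only when the marrow relapses or the patient dies, or it is never recorded, and RFS and PFS read too long.

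The second problem is that two analysts could code the same PR-to-CR converter differently. One would apply the 5% marrow threshold from the CR date. The other would keep the patient under the PR rule because CR was not reached with induction. In a set this small, that choice should not be left until outcomes are known.

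**Working it through.** No figure in the plan depends on these definitions. The sections are compared first, and the size is then estimated under stated assumptions.

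**1. Events by response state (6.9.1, 6.9.2)**

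| Finding | After PR | After CR/CRi |
|---|---|---|
| Marrow blasts | rise of more than 50% and at least 15 points, or above 25% | 5% or more |
| Extramedullary disease, including symptomatic CNS disease | event | not an event |
| Circulating blasts | event | not an event |
| Transfusion dependence | event | not an event |
| Death | event | event |

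Only the extramedullary row conflicts with the CR definition in 6.9.

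**2. Converters.** The PR marrow rule triggers at the lower of above 25%, or a rise from the maintenance-start value that is both more than 50% and at least 15 points.
- Start 5%: 5 + 15 = 20%.
- Start 8%: 8 + 15 = 23%.
- Start 10%: 10 + 15 = 25%.
- Start above 10%: only above 25%.

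A converter whose marrow returns to 5-19% has relapsed under the CR rule but has no marrow progression under the PR rule. In the other direction, transfusion dependence alone ends PFS under the PR rule and not under the CR rule.

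**3. Number of patients**
- CR/CRi: 12 is the success threshold in 8.1, and 37 × 0.40 = 14.8 are expected at the alternative. Neither is a maximum.
- Assumption: 2-10% of relapses start outside the marrow. If all 12-15 patients relapse, 12 × 0.02 = 0.24 to 15 × 0.10 = 1.5 are affected. The chance of at least one is 1 - 0.98^12 = 0.22 to 1 - 0.90^15 = 0.79. Transplant censoring and responders who never start maintenance would lower these figures.
- PRs: 37 × 0.025 = 0.9 at the mean of the Uniform(0, 0.05) that 8.1 assumes under the null, and 37 × 0.05 = 1.9 at its upper end. Only those who convert and then relapse matter.

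**4. Effect on the median.** Take exponential event times with a 5-month median, the duration of response in section 1.3. That study used a different cytarabine dose and schedule and no pembrolizumab. Then k = ln 2 / 5 = 0.1386 per month. Let s be the share of extramedullary relapses.
- Delayed by d: median = [ln 2 + ln(1 - s + s·exp(kd))] / k. With d = 12 weeks = 2.76 months, exp(kd) = 1.466. The median is 5.07, 5.17 and 5.33 months at s = 2%, 5% and 10%.
- Never counted: (1 - s)·exp(-kt) + s = 0.5, so the median = -ln[(0.5 - s)/(1 - s)] / k. This gives 5.15, 5.39 and 5.85 months.

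The 12-week figure is the marrow interval in maintenance year 1 (4.3), and it is not a ceiling. Maintenance starts 10-60 days after recovery or the CRi marrow, and four 21-day cycles add 84 days. The first scheduled maintenance marrow thus falls about 94-144 days after that point.

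**5. Sampling error.** An approximate 95% interval on a 5-month median is 5·exp(±1.96/√events): 2.8-8.8 months with 12 events and 3.0-8.3 months with 15.

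**The case against.** The strongest objection is that the marrow-only rule may be deliberate. Section 4.5.2 allows intrathecal chemotherapy for CNS disease in a patient who is still responding, so the protocol contemplates CNS disease without loss of response. The documents do not say whether that was the intent. This stands to the extent that widening the analysis definition without reconciling 4.5.2 would leave two meanings of relapse, because 4.3 and 4.6 end treatment at progression or relapse.

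A second objection is that a marrow is done whenever recurrence is suspected (4.3 and footnote 11). It does not help here: a marrow below 5% still yields no event. Section 6.9.1 also states consistency with the 2017 guideline, in a sentence placed after the PR rule. That guideline is not among the documents, so nothing is rested on it.

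Some stronger readings do not hold:
- A reader might infer that nothing but marrow relapse ends RFS. Death from any cause does as well, so some of these relapses are dated late rather than lost.
- A reader might infer that circulating blasts after CR should also be a relapse event. The CR criteria in 6.9 contain no blood-blast requirement, so the documents show only a PR-versus-CR asymmetry there.
- A reader might infer that converters are excluded from RFS. The wording in 6.9.2 can equally mean a first CR at any time after induction, and 2.4.2 and 8.3 set no induction limit.
- The gap between 4.7 and 6.6 is real but partly covered: history, examination and CBC are scheduled in follow-up, and a marrow is done on suspicion.

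**Conclusion.** The point holds and is minor. The relapse definition after CR/CRi omits a finding whose absence 6.9 requires for CR and whose presence 6.9.1 counts after PR. As written, an extramedullary relapse is dated late or missed. The converter wording is a real but small ambiguity, and for PFS its effect can go in either direction.

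Under the 2-10% assumption and a 5-month median borrowed from another regimen, the median lengthens by about 0.1-0.3 months with a 12-week delay. If such relapses are never counted, it lengthens by 0.15-0.85 months. The second range takes no account of a later death or marrow relapse in the affected patients, either of which would be counted and would reduce the shift. Both ranges lie well inside the sampling error of 12-15 events. The share is not given in the documents, so the size is illustrative, whereas the inconsistency in the text is certain.

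RFS and PFS are descriptive Kaplan-Meier secondary summaries (8.3). A reader might infer a threat to the trial's main conclusion. There is none: the primary CR/CRi endpoint, the type I error and the power do not depend on these definitions.

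**What to change.** - For the RFS/PFS analysis, define relapse for any patient who has reached CR or CRi at any time as marrow blasts of 5% or more, or new extramedullary disease, dated at the first of these. State how extramedullary disease is to be documented.
- Apply this to PR-to-CR converters from their CR date, start their RFS then, and use the same population wording in 6.9.1 and 6.9.2.
- Reconcile the definition with 4.5.2 and with the progression/relapse wording in 4.3 and 4.6. No treatment rule is proposed here.
- Reconcile 4.7 with 6.6 and footnote 5, so that relapse/progression status and date are recorded at existing follow-up visits.

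The cost is wording, a documentation standard and one CRF field, with no new visits. The downside is slightly earlier or more events. In addition, once a converter has reached CR, transfusion dependence or circulating blasts alone would no longer end PFS.
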